4.2. Exclusion Criteria

Any potential subject who meets any of the following criteria will be excluded from participating in the study.

1. Any condition or situation which, in the opinion of the investigator, may put the subject at significant risk, may confound the study results, or may interfere significantly with subject's participation in the study.
2. The use of concomitant medications known to prolong the QT/QTc interval.
3. Subject has a history of moderate or severe hepatic impairment or severe renal insufficiency unless completely resolved for more than a year. Subject has clinically significant ongoing hepatic, renal, cardiac, vascular, pulmonary, gastrointestinal, endocrine, hematologic, rheumatologic, psychiatric, or metabolic conditions (eg, requiring frequent monitoring or medication adjustments, or is otherwise unstable).

NOTE: Section 17.4, Source Documentation, describes the required documentation to support meeting the enrollment criteria.

4.3. Prohibitions and Restrictions

Potential subjects must be willing and able to adhere to the following prohibitions and restrictions during the course of the study to be eligible for participation:

1. Avoid donating blood for at least 90 days after completion (i.e., final dose administration) of the study.
2. A man who is sexually active with a woman of childbearing potential and has not had a vasectomy is advised to use a barrier method of birth control e.g., either condom with spermicidal foam/gel/film/cream/suppository or partner with occlusive cap (diaphragm or cervical/vault caps) with spermicidal foam/gel/film/cream/suppository.

3. All men must also agree not to donate sperm during the study and for 3 months after receiving the last dose of study drug.
4. For any prohibitions or restrictions related to concomitant medication see also Section 8. Prestudy and Concomitant Therapy.

5. TREATMENT ALLOCATION AND BLINDING

Treatment Allocation

Subjects enrolled in this study will participate in 2 sequential treatment periods i.e.

- DB treatment phase: a 52-Week (12-Month) placebo-controlled, double-blind, treatment period; and
- OL treatment phase: a (partially) randomized open-label treatment period (until registration)

During the DB treatment phase, subjects will receive either JNJ-54861911 (10-mg or 25-mg q.d.) based on their current treatment/dosing regimen assigned under the parent protocol (54861911ALZ2002 or any future studies) as described in Section 6, Dosage and Administration.

In the OL phase, subjects who received placebo in the DB treatment period will be automatically randomized to active treatment (JNJ-54861911 5-mg or 25-mg q.d.) as described in Section 6, Dosage and Administration. Subjects who were receiving 10 mg q.d. JNJ-54861911 in DB treatment phase will have their dose reduced to 5 mg q.d., while subjects who were receiving 25 mg q.d. will continue to receive that dosage.

Procedures for Randomization

Subjects who received placebo during the DB treatment phase will be randomly assigned with equal chance to one of two treatment groups in the OL phase based on a computer-generated randomization schedule prepared before the study by or under the supervision of the sponsor. The randomization will be balanced using permuted blocks across the 2 treatment groups.

For both DB and OL treatment phases, an interactive web response system (IWRS) will be utilized to assign the blinded study drug kits in this study. For DB treatment phase study drug kits will be assigned based on their treatment allocation in 54861911ALZ2002 study; for non-placebo subjects in OL phase, subjects who were receiving 10 mg q.d. JNJ-54861911 in DB treatment phase will have their dose reduced to 5 mg q.d., while subjects who were receiving 25 mg q.d. will continue to receive that dosage.

The blister packs and kit assignment will be managed by the IWRS for both the blinded and unblinded phase of the study.

Since the investigator will be blinded to treatment assignment in the DB treatment phase, the IWRS will automatically determine the appropriate medication kits to assign. Subjects who were receiving 10 mg q.d. JNJ-54861911 in the DB treatment phase will have their dose reduced to 5 mg q.d. in the OL phase, while subjects who were receiving 25 mg q.d. will continue to receive

that dosage. Subjects receiving placebo in the DB treatment phase will be randomized with equal chance to either 5 mg q.d or to 25 mg q.d. Neither the randomization number nor the fact that a subject was randomized for OL phase will be known to the investigator, thus allowing the blind to be maintained while DB treatment phase is still ongoing.

The total number of subjects on placebo to be randomized to active treatment in this study will be determined by the number of subjects enrolling who previously were allocated to placebo in 54861911ALZ2002 study.

Central randomization will be implemented in conducting OL phase of this study for subjects previously receiving placebo. Central randomization minimizes the imbalance in the distribution of the number of subjects across treatment. Based on the algorithm, the IWRS will assign a unique treatment code, which will dictate the treatment assignment and matching study drug kit for the subject.

Central randomization will be used to avoid bias in the assignment of subjects to treatment, to increase the likelihood that known and unknown subject attributes (e.g., demographics and baseline characteristics) are evenly balanced across treatment groups.

During the DB treatment phase (placebo-controlled), both the investigator and the subject will be blinded to reduce subjective influences on safety and tolerability data.

Blinding

The investigator will not be provided with randomization codes for the parent protocol (54861911ALZ2002 study) or the randomization numbers for this study until all subjects of the parent protocol have completed DB treatment phase and subsequent database lock or freeze has occurred. The codes will be maintained within the IWRS, which has the functionality to allow the investigator to break the blind for an individual subject.

Under normal circumstances, the blind should not be broken by the investigator until all subjects from the 54861911ALZ2002 study enrolled in this study have completed DB treatment phase of the study and the DB treatment phase database for those subjects is finalized.

Otherwise, the blind should be broken by the investigator only if specific emergency treatment/course of action would be dictated by knowing the treatment status of the subject. In such cases, the investigator may, in an emergency, determine the identity of the treatment by contacting the IWRS. It is recommended that the investigator contact the sponsor or its designee if possible to discuss the particular situation, before breaking the blind. Telephone contact with the sponsor or its designee will be available 24 hours per day, 7 days per week. In the event the blind is broken, the sponsor must be informed as soon as possible. The date, time, and reason for the unblinding must be documented by the IWRS, in the appropriate section of the case report form (CRF), and in the source document. The documentation received from the IWRS indicating the code break must be retained with the subject's source documents in a secure manner.

Subjects who have had their treatment assignment unblinded are not required to return for scheduled evaluations except for the End-of-Treatment visit (Follow-up visit).

When the parent study (e.g. 54861911ALZ2002 and potential future Phase 1b and 2 studies) is completed and its clinical database is closed, the randomization codes from the parent study will be released to the sponsor study team. Thus the sponsor will be unblinded at that time, but the investigator and subjects will continue to be blinded to treatment during the DB treatment phase.

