- ^j CSF samples (12 mL/sample; baseline and on treatment samples) should be taken at approximately the same time of day (with an allowable window of 3 hours), with the on treatment samples being collected postdose. In Treatment Period 2 (>52 weeks) it is intended to collect if possible on-treatment CSF samples every 96 weeks until study completion. Subjects may opt not to have these punctures being performed. CSF samples collected will be used for biomarker and PK analysis.
- ^k Only if no on-treatment CSF sample was collected under the parent protocol (54861911ALZ2002 study).
- ^l Only during the first 12 week visit of the open-label treatment phase.

- ^m Ophthalmologic examination will be performed only if: 1) if there was an abnormality present at the screening/baseline examination; 2) if the investigator detects new ophthalmological findings or visual symptoms; 3) if OCT reveals new findings. The ophthalmologic examination should be performed by the same ophthalmologist who completed the initial ophthalmologic examination at screening/baseline.
- ⁿ If a subject discontinues study treatment the subject will be asked to complete the Week 52 assessments, including CSF sampling, if not yet obtained earlier. In addition, and at a minimum the subject will be asked to complete the End-of-Treatment Visit (Follow-up visit) as per Time and Events Schedule.
- ^o At Week 52 subjects will be dosed according to treatment allocation assigned to in Treatment Period 1. Randomization to Treatment Period 2 and dispensation of study medication for Treatment Period 2 will only be performed following completion of all week 52 assessments.
- ^p Whenever a skin lesion not previously documented is reported by the study subject or the investigator, in addition to a dermatological exam by the dermatologist, digital images of the lesion will be acquired at the time the lesion is discovered and at follow-up visits with a frequency which is deemed appropriate by the sponsor of the study. Duration of follow-up of newly documented skin lesions or depigmentation might extend beyond the treatment period, as judged adequate by the sponsor to ensure the safety of subjects in this study.
- ^q Additional MRI scans may be collected based on emerging safety data with a frequency as recommended by the DRC.
- ^r At sites where OCT is available.
- ^s 2 to 4 hours postdose.

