- Drop one active dose level (subjects allocated in the OL phase to the dose level dropped will be reassigned in the OL phase to the remaining active dose level)
- Assign all placebo subjects to a single active dose level

During the treatment phases of this study dispensing and redispensing of their study medication will take place at the visits indicated in the Time and Events Schedule. On Days of re-dispensing subjects will hand in their medication package dispensed previously and drug accountability will be performed.

Following last dosing, subjects will hand in their study medication received previously and final drug accountability will be performed.

During the study (DB and OL treatment phases) subjects will self-administer q.d. study drug (JNJ-54861911/placebo) with a glass of non-carbonated water, after completion of breakfast or a light snack, during the morning hours, according to the instructions provided by the investigator. During scheduled visits subjects will self-administer their study medication on site. On Day 1, study drug administration will be administered following completion of all predose assessment and will not be limited to morning hours.

If a subject realizes before 2:00 PM that he/she forgot to take their daily dose, he/she will be instructed to take the daily dose even if late (before 2:00 PM).

If a subject realizes after 2:00 PM he/she forgot to take his/her daily dose, he/she will be instructed not to take any dose during that day, but resume dosing the following day.

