9.1.5. End-of-Treatment Visit (Follow Up Visit)

An End-of-Treatment visit (or phone call) for a safety assessment should take place approximately 30 days after the last dose of study drug. This will consist of at least a review of Adverse Events and concomitant medication and C-SSRS assessment (since the last visit). The study is considered completed with the last End-of-Treatment safety assessment for the last subject participating in the study or upon a decision by the sponsor to terminate the study.

Investigators may recontact the subject to obtain long-term follow-up information to determine the subject's safety or survival status (refer to Section 16.2.3, Informed Consent).

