10.2. Discontinuation of Study Treatment

If a subject's study treatment must be discontinued before the end of the treatment regimen, this will not result in automatic withdrawal of the subject from the study.

The following specific individual rules for stopping study treatment will apply:

- Mean QTcF interval of > 500 msec if confirmed upon repeat ECG, and/or mean QTcF increase versus baseline of > 60 msec if confirmed upon repeat ECG (all triplicate recordings).
- The investigator believes that for safety reasons (e.g., adverse event) it is in the best interest of the subject.
- Liver enzyme elevation between Weeks 52 and 64, including any of the following:
 - ALT or AST $>5\times$ ULN
 - ALT or AST $>3\times$ ULN and total bilirubin $>2\times$ ULN or INR >1.5
 - ALT or AST $>3\times$ ULN with the appearance of fatigue, nausea, vomiting, right upper quadrant pain or tenderness, fever, rash, and/or eosinophilia $>5\%$
- Liver enzyme elevation after Week 64, including any of the following:
 - ALT or AST $>8\times$ ULN
 - ALT or AST $>5\times$ ULN for more than 2 weeks
 - ALT or AST $>3\times$ ULN and total bilirubin $>2\times$ ULN or INR >1.5
 - ALT or AST $>3\times$ ULN with the appearance of fatigue, nausea, vomiting, right upper quadrant pain or tenderness, fever, rash, and/or eosinophilia $>5\%$

Re-initiation of study treatment should only be done after consultation with the sponsor medical monitor and in mutual agreement between the sponsor and the study center. If a subject permanently discontinues study treatment before the end of the treatment phase, the subject will be asked to complete the Week 52 assessments, including CSF sampling, if not yet obtained earlier. At a minimum, the subject will be asked to complete the End-of-Treatment Visit (Follow-up visit) as per the Time and Events Schedule.

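### Section 5 excuses any unblinded subject from scheduled evaluations, so one still on study drug after an emergency code break has only optional safety assessments before Week 52

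*Protocol*

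**What the plan says.** Until the double-blind (DB) database is final, the investigator should break the blind "only if specific emergency treatment/course of action would be dictated by knowing the treatment status of the subject" (Protocol Section 5, Blinding). The same section then sets the follow-up rule: "Subjects who have had their treatment assignment unblinded are not required to return for scheduled evaluations except for the End-of-Treatment visit (Follow-up visit"). It does not mention whether the subject is on or off drug.

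Section 9.1.5 defines the visit that is kept: "An End-of-Treatment visit (or phone call) for a safety assessment should take place approximately 30 days after the last dose of study drug". Its minimum content is adverse events, concomitant medication and C-SSRS.

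Other sections bear on the same subject:

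- Section 6: "dispensing and redispensing of their study medication will take place at the visits indicated in the Time and Events Schedule". It also makes open-label (OL) randomization and dispensing wait until every Week 52 assessment is done. Section 9.1.3 and footnote o of the Time and Events Schedule repeat this.
- Section 10.2: if treatment must be stopped early, "this will not result in automatic withdrawal of the subject from the study". A subject who "permanently discontinues study treatment before the end of the treatment phase, the subject will be asked to complete the Week 52 assessments". The floor follows: "At a minimum, the subject will be asked to complete the End-of-Treatment Visit".
- Time and Events Schedule, footnote n: "If a subject discontinues study treatment the subject will be asked to complete the Week 52 assessments". The note closing Section 9.1.3 and Section 10.3 make the same request, the latter for subjects who withdraw.
- Sections 9.2.1 and 12.3.1: adverse events are reported throughout participation, not only at visits.

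**The concern.** The waiver would be coherent if a code break ended treatment. The protocol never says that it does. A subject who stays on drug is then excused from scheduled evaluations, and the single remaining contact cannot be dated until dosing ends. Section 5 asks less of that subject than Section 10.2 asks of one who has stopped.

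The primary objective is long-term safety and tolerability (Section 2.1), and the 52-week DB phase is the placebo-controlled part of this study. Permitted code breaks before lock are emergencies, so the subjects concerned are probably selected by a safety event, and missing scheduled data from them is unlikely to be ignorable. Loss of the blind is a weak reason to forgo laboratory tests, ECG and MRI, because these are tested or read centrally (Sections 9.2.4, 9.2.8, 9.2.9).

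The sentence is also wider than emergencies. As worded, it reaches OL subjects whose DB allocation is disclosed on request after lock (Sections 3.3 and 11.6), although Section 9.1.4 has all OL subjects undergo scheduled safety laboratory tests.

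**Working it through.** The protocol gives no figure for this point. The check sets the rules side by side and counts assessments from the Time and Events Schedule.

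**1. Does a code break end treatment or participation?** The stopping rules in Sections 3.4.1 and 10.2 cover QTcF, the investigator's safety judgment and liver enzymes; Section 3.4.1 adds the withdrawal criteria. Section 10.3 lists loss to follow-up, withdrawn consent or assent, death and noncompliance. Unblinding is in none of them, so a subject can be unblinded and still on drug.

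**2. What remains required for that subject?**

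- Visits after Day 1 in the DB phase: Weeks 8, 12, 16, 24, 36, 52 = 6.
- Visits with dispensing: Weeks 12, 24, 36, 52 = 4. Laboratory-only visits: 6 − 4 = 2 (Weeks 8, 16).
- Supply intervals: Day 1 to Week 12, 12 to 24 and 24 to 36 are 12 weeks each; 36 to 52 is 16 weeks. Continued dosing therefore needs attendance at Weeks 12, 24 and 36.
- Entry to the OL phase needs the Week 52 assessments.

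**3. What becomes optional for an on-drug subject who continues to OL?** Count the scheduled occasions after the code break and subtract Week 52, which Section 6 secures.

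| Assessment | Scheduled after Day 1 (weeks) | Break before Week 8 | Break between Weeks 24 and 36 |
|---|---|---|---|
| Hematology/chemistry | 8, 16, 24, 36, 52 | 5 − 1 = 4 | 2 − 1 = 1 |
| Adverse event review | 12, 24, 36, 52 | 4 − 1 = 3 | 2 − 1 = 1 |
| C-SSRS | 12, 24, 36, 52 | 4 − 1 = 3 | 2 − 1 = 1 |
| ECG, MRI, dermatologic examination, RBANS (each) | 24, 52 | 2 − 1 = 1 | 1 − 1 = 0 |
| CDR | 52 | 1 − 1 = 0 | 1 − 1 = 0 |

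**4. What of subjects who stop drug or withdraw?** Footnote n and Sections 9.1.3, 10.2 and 10.3 ask them for the Week 52 set. Section 5 requires only the End-of-Treatment contact. Sections 10.2 and 10.3 and footnote n have that same contact as their minimum, so the rules differ in strength.

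**5. Does event-driven follow-up fill the gap?** Persisting abnormalities (Section 9.2), new skin lesions (9.2.6) and unresolved serious events (12.3.2) are still followed. The liver work-up in Attachment 1 starts when per protocol assessments show ALT or AST at or above 3 times the upper limit of normal. It follows up a known elevation but does not replace the draws that would find a new one.

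**The case against.** The strongest reply is that the sentence follows the emergency code-break paragraph and keeps only a visit timed from the last dose, so it presupposes that treatment has ended. It is also permissive: it forbids no visit. Dispensing, the Week 52 condition for OL drug and continuous adverse event reporting close much of the gap. Analyses are descriptive with no hypothesis test (Sections 2.2, 11), and code breaks should be rare.

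Most of this stands and sets the size of the point. A reader might infer more, and the documents do not support it:

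- That a subject unblinded before Week 8 could be dosed unobserved for 52 − 8 = 44 weeks. Drug in hand lasts about 12 weeks (16 from Week 36), apart from visit windows, so continued dosing brings the subject to the site.
- That the only DB-phase CDR after Day 1 is always lost. It falls at Week 52, which is a condition for OL drug and is requested of subjects who stop or withdraw.
- That Section 5 flatly contradicts Section 10.2. The Week 52 set is a request there, and the minimum is shared.

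The reply does not supply the missing condition. That treatment has ended is an inference; no section says it. Attending to collect drug does not make the evaluations at that visit required, and Weeks 8 and 16 have no dispensing at all.

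**Conclusion.** The point holds in a limited form. A stated rule, rather than an omitted detail, makes the pre-Week 52 evaluations optional for a subject who stays on drug after an emergency code break and continues to OL. The loss ranges from the full pre-Week 52 set counted above (break before Week 8), through the Week 36 laboratory draw, adverse event review and C-SSRS (break between Weeks 24 and 36), to nothing before Week 52 for a break after Week 36.

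This rests on a literal reading of Section 5 and on the absence of unblinding from the stopping and withdrawal lists. That emergency code breaks track safety events is likely but not stated. The protocol gives no number of code breaks, so neither the number of subjects affected nor the size or direction of any bias can be derived. It is a correction worth making, not a threat to the design.

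**What to change.** In Section 5, limit the sentence to emergency code breaks and reconcile it with Sections 9.1.3, 10.2 and 10.3:

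- subjects who remain on study drug under the existing rules stay on the existing schedule of evaluations;
- subjects who stop drug or withdraw follow Sections 10.2 and 10.3, with the Week 52 assessments requested if not yet obtained, plus the End-of-Treatment visit.

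Whether an unblinded subject stays on drug is left to the existing rules; no change to them is proposed. Flag site-rated assessments made after the code break, whose date Section 5 already has recorded in the CRF.

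The cost is one sentence and a cross-reference, with no new procedure. For a subject still on drug it means at most two laboratory-only visits (Weeks 8 and 16) beyond drug pick-up. For a subject who stops, it adds nothing to Sections 10.2 and 10.3. Some RBANS and CDR data would be collected unblinded. Flagged data can be set aside in analysis, whereas data never collected cannot be recovered.

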6. DOSAGE AND ADMINISTRATION

Study medication will be provided as JNJ-54861911 tablets, strengths 5-mg, 25-mg and matching placebo. Study medication will be blister packed. All tablets (JNJ-54861911/placebo) are physically identical.

A study-site investigational product manual including instructions for dispensing, storage (on site and at home) and intake of the study medication will be supplied to the study-site.

Study-site personnel will instruct subjects on how to store study drug for at-home use as indicated for this protocol.

Eligible subjects enrolled in this study will participate in 2 sequential treatment periods:

- **Double-blind treatment phase:** a 52-week (12 Months) placebo-controlled, double-blind treatment phase. Eligible subjects enrolled will receive either JNJ-54861911 (10-mg or 25-mg q.d.) or placebo (q.d.). Subjects will continue on their current treatment regimen assigned under the parent protocol (placebo, 10-mg or 25-mg q.d. JNJ-54861911). Subjects who received an active dose different from 10-mg or 25-mg JNJ-54861911 under the parent protocol will be receiving the closest dose available in the DB treatment phase (i.e. subjects receiving 50 mg in study 54861911ALZ2002 will be assigned to 25 mg JNJ-54861911).
- **Open-label phase:** an open-label treatment phase during which subjects who received placebo in the DB treatment phase will be randomized to one of two JNJ-54861911 dose levels:
 - 5-mg q.d. JNJ-54861911; or
 - 25-mg q.d. JNJ-54861911

Randomization (for placebo subjects) to OL phase and dispensing of study medication for OL phase will only be performed following completion of all Week 52 assessments.

During the DB treatment phase, study drug kits will be assigned based on their treatment allocation under the parent protocol; for nonplacebo subjects in the OL phase, subjects who were receiving 10 mg q.d. JNJ-54861911 in the DB treatment phase will have their dose reduced to 5 mg q.d., while subjects who were receiving 25 mg q.d. will continue to receive that dosage.

During the course of the study, the Sponsor will have the option based on recommendations by the DRC or based upon newly emerging safety, biomarker or efficacy data from ongoing or completed JNJ-54861911 studies, to revise the dose levels for OL phase to:

- Maintain the 2 selected active dose levels (equal randomization of the placebo treated subjects)
- Adjust the dose level for one or both of the selected active doses
- Drop one active dose level (subjects allocated in the OL phase to the dose level dropped will be reassigned in the OL phase to the remaining active dose level)
- Assign all placebo subjects to a single active dose level

During the treatment phases of this study dispensing and redispensing of their study medication will take place at the visits indicated in the Time and Events Schedule. On Days of re-dispensing subjects will hand in their medication package dispensed previously and drug accountability will be performed.

Following last dosing, subjects will hand in their study medication received previously and final drug accountability will be performed.

During the study (DB and OL treatment phases) subjects will self-administer q.d. study drug (JNJ-54861911/placebo) with a glass of non-carbonated water, after completion of breakfast or a light snack, during the morning hours, according to the instructions provided by the investigator. During scheduled visits subjects will self-administer their study medication on site. On Day 1, study drug administration will be administered following completion of all predose assessment and will not be limited to morning hours.

If a subject realizes before 2:00 PM that he/she forgot to take their daily dose, he/she will be instructed to take the daily dose even if late (before 2:00 PM).

If a subject realizes after 2:00 PM he/she forgot to take his/her daily dose, he/she will be instructed not to take any dose during that day, but resume dosing the following day.

